**Focus Groups and Usability Testing:** Twenty high-risk adolescents will be recruited to participate as test users in the development phase to give us initial reactions to mockup of modules, and a subgroup of 10 of these participants will be recruited to participate in preliminary usability testing of the modules. Feedback from usability testing will be used to inform adaptations to the app. The prototype app will then be evaluated in an efficacy trial with 380 additional high-risk adolescents. The primary outcomes of the evaluation-testing phase will be changes in adolescent substance use attitudes and behaviors and emotion regulation measured at three time points: baseline, 4 weeks post- baseline (end of treatment), and three months post-baseline. The proposed efficacy trial will evaluate the extent that the Qlarity app influences positive behavior change and will provide power estimates for later larger scale evaluation.

**Efficacy Trial:** Based on our power calculations, we will recruit 380 adolescents who are involved in the juvenile justice system. We have a long history of cooperation with the DHS and have well-established recruitment procedures. Eligible adolescents and their consenting parents will be recruited on a continual basis and will be included in the study for 3 months post-baseline. The participants will be randomly and equally assigned to the Qlarity condition ( $n = 190$ ) or the DC standard treatment condition ( $n = 190$ ) following adolescent assent and parent consent. Given that all youth will be involved in the juvenile justice system, we will assess all services offered and accessed by youth in both conditions.

Based on our prior experience, we expect many of the youth to be under orders to be participating in urine screening or other intervention services through DHS. Data from our current and prior studies with this population suggest that despite receiving random urine screens as part of their probationary status, 90% of youth are involved in ongoing alcohol, tobacco or other drug use (79% alcohol; 68% tobacco; 81% marijuana, and 53% other drug; 90% positive for one or more substance) at the time of referral. We will track additional services, including mandated urine screens, via official DHS reports and using a services utilization measure at each follow-up time point.

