health-related groups (e.g., Narcotics or Alcoholics Anonymous, or physical health groups). For each type of service accessed, there are questions regarding frequency, reason for the service (e.g., physical, mental health, substance-use related), insurance coverage and out-of-pocket expenses. The Five Facet Mindfulness Questionnaire is a 36-item self-reported questionnaire that queries aspects of mindfulness such as non-judgment. The Adolescent Attitudes Questionnaire is a measure of attitudes and beliefs regarding drug and alcohol that was adapted from an interview developed to test 12 mediators of drug use in adolescents. For this study, we will use the normative beliefs, lifestyle incongruence, beliefs about consequences, and commitment scales. The Emotion Regulation Scale is a 36-item self-report questionnaire designed to assess multiple aspects of emotion dysregulation. Program navigation and usability will be assessed for all participants and will include reports of: 1) ease of use, 2) perceived benefits of using the app, 3) likeability, and

4) suggestions for product development and modifications. Participants will provide ratings on product satisfaction and usability on a 7-point Likert Scale. Qualitative data gathered from the focus groups will be recorded and evaluated with the goal of identifying challenges to using the app, product satisfaction, and suggested product modifications. In addition to qualitative data gathered during the pilot evaluation study, login tracking information from the app will be used to assess each participant's: 1) frequency and duration of app use and 2) number of modules completed. These data will be used to evaluate treatment engagement and adherence.

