**Statistical design and power overview:** This project will test the efficacy of the Qlarity app in Year 2 with a randomized trial that nests multiple assessments nested with 380 youth within each of two conditions. Half of the participants will receive the Qlarity app intervention and half will maintain business-as-usual. We hypothesize that Qlarity app will increase youth's emotional regulation, mindfulness and self-efficacy and decrease alcohol, tobacco, and other drug use. Within this study design, we will test for main effects, moderation, mediation, and acceptability of the Qlarity app intervention and expect to detect effect sizes of 0.25 standard deviations. Program feasibility will be demonstrated via significant pre-post differences, a high and consistent level of app use, and a high degree of youth satisfaction ratings. See Human Subjects Statistical Design and Power section for complete details.

**Feasibility benchmarks:** Program feasibility will be demonstrated by the achievement of the following benchmarks: (a) significant pre-post increases (e.g., Cohen's  $d > .35$ ) in emotional regulation, mindfulness, and self-efficacy, (b) significantly greater decreases in alcohol, tobacco, and other drug use for Qlarity participants; (c) a high consistent level of app usage (e.g., over 70% of users used the app at least 12 times over the 12 weeks); and (d) a high degree of youth satisfaction and ratings of app acceptability and usability (mean ratings  $> 4.0$  on the 5-point scale). Benchmarks are based on meta-analysis quantitative methods that recommend effect sizes of at least  $d > .25$  to demonstrate educationally meaningful change; a desire to show at least an average of weekly app use by a majority of participants; and a level of participant satisfaction that meets or exceeds that of Phase I.

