**Mediation effects.** Growth-curve models implemented in an SEM framework will be used to explore whether observed condition effects on tobacco, alcohol, and drug use are mediated by adolescent attitudes and mindfulness. Following Preacher et al., models will be constructed by individually fitting growth models for mediators and outcomes using the growth curve model-building sequence described above to develop the best longitudinal change model. Then mediator and outcome growth curves will be combined in a single model. We will test whether (a) condition predicts change in each mediator, (b) condition predicts change in each outcome, (c) mediator change predicts outcome change, and (d) the condition effect on the outcome is significantly weaker when controlling for level or change in the mediator. Significance of indirect effects will be tested using bias-corrected bootstrapped confidence intervals.

**Process analyses.** A critical element to the program evaluation is the acceptability of the intervention to the target population, which will be assessed via rate of attrition, level of program

use, and degree of program satisfaction. Dose-response analyses will be conducted to examine the degree to which treatment engagement and retention (e.g., frequency and duration of app use, number of modules completed) predict change in the outcome measures at the post-intervention and follow-up assessments. Canonical correlation analyses will be used to examine the association between the dosage measures and outcome measures within the Qlarity condition. We will also test the hypothesis that those participants who report greater satisfaction with the intervention will have greater improvement in baseline-post scores using residual gain score analyses. Lastly, treating participant satisfaction as a process variable, we will examine the correlations between the satisfaction ratings and the amount of treatment engagement/retention.

**Missing data.** Missing data in outcome measures may result from dropout or item non-response. The mixed- growth models described above make use of maximum likelihood estimates and allow for use of all available outcome data from all assessments, reducing bias and increasing power. In general, maximum likelihood procedures, as well as imputation methods, will be used as they can provide unbiased estimates even in instances of substantial attrition. Multiple imputation procedures will follow best-practice recommendations.

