**Power considerations.** The assumptions for the power estimates include a sample size of 380 participants, Type II error rate of 20% ( $\beta = .20$ ) and a 2-tailed alpha = .05. Power estimates for multilevel growth models require assumptions that are not easily established in longitudinal studies (e.g., complete data, homogeneous random-effects covariance structures within conditions). Thus we rely on the fact that power for multilevel growth models has been shown to surpass that of the mixed-model ANCOVA. The proposed growth models, then, will detect smaller differences between conditions than the ANCOVA models on which power estimates were based. Allowing for intent-to-treat analyses that makes use of all available data using missing data techniques described above and a pretest covariate  $r^2 = .25$ , there is sufficient power to detect main effects for condition of Cohen's  $d = .25$  (small effect size) and detect condition by moderator effects of  $d = .35$  (small to medium effect). The smallest subsample expected for decomposition of significant moderating effects is approximately 150 minority participants (75 per condition) which will provide sufficient power ( $>.80$ ) to detect condition effects of  $d = .40$  (medium effect). The study is also powered to detect small to medium between condition effect size differences (ORs = 2.05 – 2.25) for the logistic regression models predicting an estimated 15-20% substance use abstinence rates at follow-up. Using mediation effect size guidelines from Kenny for a model containing a dichotomous independent variable and a continuous mediator, effect sizes of .02, .15, and .40 derived from the product of  $d$  and  $r$ , represent small, medium, and large effect sizes respectively. Assuming small to moderate effects for the indirect pathway ( $r = .20$ ), the proposed sample size has sufficient power ( $>.94$ ) to detect small effect sizes or greater ( $dr = .04$ ) for tests of mediation. Process analyses involving correlation coefficients will have adequate power to detect small to medium effects ( $r = .20$ ).

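### Three outcome domains are all called primary, with no hierarchy, multiplicity adjustment or success rule, so the .05 error rate and the stated power belong to no single efficacy test

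*Combined protocol and SAP*

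**What the plan says.** All references are to the combined protocol and SAP.

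- **Primary outcomes.** Under Stage 2, the paragraph on focus groups and usability testing states: "The primary outcomes of the evaluation-testing phase will be changes in adolescent substance use attitudes and behaviors and emotion regulation". These are to be measured at baseline, 4 weeks and 3 months. No variable or time point is singled out.
- **Instruments.** For the attitudes questionnaire, the Measures paragraph says "we will use the normative beliefs, lifestyle incongruence, beliefs about consequences, and commitment scales". It does not say whether these four scales are tested separately or as one score. Emotion regulation has one questionnaire.
- **Hypotheses.** The statistical design and power overview expects Qlarity to increase "emotional regulation, mindfulness and self-efficacy and decrease alcohol, tobacco, and other drug use". This list adds mindfulness and self-efficacy and leaves out attitudes.
- **Mediation.** The mediation paragraph explores whether effects on substance use "are mediated by adolescent attitudes and mindfulness".
- **Tests.** The main-effects paragraph gives a condition-by-time interaction in a growth model for most hypotheses, plus a logistic regression of abstinence at 3 months. The Study Design paragraph has both 7-day and 30-day abstinence.
- **Error rates.** The power paragraph gives "a 2-tailed alpha = .05" and 80% power. It quotes d = .25 for main effects of condition, and odds ratios of 2.05–2.25 for the abstinence models.

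**The concern.** The trial is described as testing efficacy, so a reader will expect a .05 error rate to apply to the efficacy conclusion. With several primary outcomes and no rule for combining them, it applies only to each test taken alone. After the data are seen, nothing in the text prevents a single significant result among several from being presented as the primary finding.

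The difference between the primary-outcome sentence and the hypothesis list makes this harder to settle, because a reader cannot tell from the two together which result decides efficacy. For the same reason, the d = .25 power cannot be tied to a particular continuous outcome.

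**Working it through.** **1. The plan's own power figure.** Inputs from the power paragraph are N = 380 (190 per arm with equal allocation), d = .25, pretest r² = .25, two-sided alpha .05 and ANCOVA as the basis.

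- Residual SD = √(1 − .25) = .866.
- Standard error = .866 × √(2/190) = .0889.
- d / SE = .25 / .0889 = 2.814.
- Power = Φ(2.814 − 1.960) = .803 (.801 with the t distribution).

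The stated 80% therefore reproduces, for one test at .05.

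**2. How many tests?** The documents give no number. Three counts are reasonable:

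- *Three*: one test per named domain.
- *Five*: one attitude score, three substances (alcohol, tobacco, other drugs) and emotion regulation.
- *Eight*: as five, but with the four attitude scales tested separately (4 + 3 + 1).

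Separate abstinence tests would add to any of these.

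**3. Chance of at least one false positive if no outcome is affected.** Each test is taken at two-sided .05. For independent tests:

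- Either direction: 1 − .95^k.
- Favouring Qlarity: 1 − .975^k.

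For k = 8 these are 1 − .95^8 = .337 and 1 − .975^8 = .183. For tests with a common correlation ρ, the either-direction figure is

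1 − ∫ φ(u) [Φ((1.96 − √ρ·u)/√(1−ρ)) − Φ((−1.96 − √ρ·u)/√(1−ρ))]^k du.

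The favourable-direction figure drops the second Φ term. The documents give no correlation, so ρ is an assumption and a range is shown.

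| Tests | Either direction, ρ = 0 | ρ = .3 | ρ = .5 | ρ = .7 | Favouring Qlarity, ρ = 0 | ρ = .5 |
|---|---|---|---|---|---|---|
| 1 | 5.0% | 5.0% | 5.0% | 5.0% | 2.5% | 2.5% |
| 3 | 14.3% | 13.6% | 12.5% | 10.9% | 7.3% | 6.3% |
| 5 | 22.6% | 20.9% | 18.3% | 14.8% | 11.9% | 9.1% |
| 8 | 33.7% | 30.0% | 25.0% | 19.1% | 18.3% | 12.5% |

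**4. Power if all three domains stay primary.** At alpha = .05/3 = .0167 the critical value is 2.394. Power = Φ(2.814 − 2.394) = .66 (.663 normal, .659 t). This is the level of Holm's first step; later steps use a larger alpha.

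**5. Does naming substance use settle it?** Not without more detail. Three substances tested separately give up to 14.3% again. The power also depends on the form of the variable. The d = .25 figure is for a continuous measure. The abstinence model is powered for odds ratios of 2.05–2.25, which by ln(OR) × √3/π correspond to d of about .40–.45.

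**The case against.** A fair defence has five parts.

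- **The count is not in the plan.** This stands. A reader might infer that at least eight primary tests are planned, but that needs the four attitude scales to be tested separately, which the text does not say. Three or five are equally open.
- **The larger percentages are not false claims of benefit.** This also stands. A reader might take 25–34% as the chance of a false efficacy claim. It is the chance of any significant difference, harmful or beneficial, for eight tests. The figure for claims favouring Qlarity is 12.5–18%.
- **No any-one-wins rule is written, and .05 appears only as a power assumption.** True, but no other level and no other rule is given. The feasibility benchmarks can be read as all having to be met, yet they define feasibility rather than efficacy. The trial is also meant to inform a later, larger evaluation. That softens the need for strict control but does not remove it from a trial presented as testing efficacy.
- **The lists do not strictly conflict.** Largely right. The overview states hypotheses rather than primary outcomes, and a variable can be both an outcome and a mediator. The mediation steps themselves test whether condition changes each mediator. What remains is a need to align the wording.
- **Power is attached to something.** Right in part: the odds ratios are tied to abstinence at follow-up. The d = .25 figure is tied to no named outcome.

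The overview also refers to a human-subjects section on design and power for full details. The Data Analysis section appears to be that material, but the text does not confirm it.

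**Conclusion.** The concern holds in a limited form. Several domains are primary, and the text supplies no hierarchy, adjustment or success rule; that does not depend on any count. Its size does. On the smallest reasonable count, the error rate is two and a half to nearly three times the nominal level (12.5–14.3% against 5%). With eight tests it is five to nearly seven times (25–34%). The ratios for errors favouring Qlarity are similar.

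These figures assume that every test is run at two-sided .05, that no outcome is truly affected, that one significant result would be taken as success, and that correlations lie between 0 and .5. At .7 they fall to 10.9% for three tests and 19.1% for eight. The sample size calculation itself is sound for one test. The plan should be changed, but the documents do not show a defect that invalidates the trial.

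**What to change.** Before any unblinded analysis, amend the primary-outcome sentence, the statistical design and power overview, and the main-effects paragraph.

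1. Name one primary variable, tested at two-sided .05, giving its instrument, substance definition, time point and test. A substance-use measure fits the stated aim of behavior change. Two forms match the existing analyses:
   - one continuous composite analysed with the growth model. The d = .25 power then applies, on the plan's own argument that growth models are at least as powerful as ANCOVA;
   - any-substance abstinence at 3 months analysed by logistic regression, with one recall window chosen and the role of the urine screen stated. The odds ratios of 2.05–2.25 then apply and should be quoted instead of d = .25.
2. Make attitudes, emotion regulation, mindfulness and self-efficacy secondary, tested with Holm's procedure. State whether attitudes count as one score or four. Attitudes can remain a mediator as well.
3. Align the primary-outcome sentence with the hypothesis list.
4. If the sponsor prefers to keep all three domains primary, define one variable for each, apply Holm across them and restate the power: about .66 for d = .25 at alpha .0167 with N = 380.

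The cost is wording only, with no added participants. The downside is that the secondary outcomes lose some power under Holm.

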### **Overview of the Proposed Intervention Conditions**

We propose to randomize youth into one of two conditions, outlined below.

**Qlarity.** Subjects randomized to Qlarity will be provided in-person assistance in loading the Qlarity app onto their phone immediately following their baseline interview and assessment. Once the app is loaded onto their phone, participants will generate a username and password. The proposed modules will each include a teaching and a practice component that uses mindfulness techniques to reduce or avoid substance use. Modules will be “unlocked” in ascending order as participants move through the program (i.e., module 2 will be “unlocked” after completion of module 1, etc.).

**Drug Court, Group Therapy and Case Management (DC).** The DC youth will receive the usual services provided by the DHS for youth who present with drug and alcohol use, which includes involvement in drug court, and case management services for the youth and their parents that span the duration of the youth’s probation or formal accountability contract. The drug court and case management services are provided by probation officers through the DHS. The DHS will manage each case and will make all decisions on referrals to community resources, including individual therapy, family therapy, mandated urine screens, and/or inpatient or outpatient substance use treatment that might occur in addition to the typical youth skill building groups and case management services. None of the usual services that youth in the respective study conditions receive will be affected by their participation in the study. We will track the youths’ and parents’ use of services as part of the interviews with a service utilization measure and official DHS reports of urine screens at each assessment. With these data, we will examine the type and length of treatment received for youth in both conditions, as well as the timing and outcome of urine screens over the course of the study. This services utilization measure has been used in previous work and has been useful for examining treatment impact.

## Data Collection Procedures

**Overview and timeline for the proposed data collection:** In the proposed study, a total of at least 380 youth will be recruited and baseline assessed for the study. We anticipate that approximately 10% of these will fail to complete the study, resulting in a sample of at least 342 youth with complete data and an intent-to-treat analysis strategy which will include all 380 youth. We will conduct baseline assessments and follow-up assessments at treatment completion (1 month), and at 3 month post-baseline.

**Assessments:** The *baseline assessment* primarily measures youth risk factors, as well as past and current substance use, and will consist of an in-person interview including questionnaires with the youth.

The *treatment completion (1-month), and 3-month assessments* are aimed at assessing short and longer term outcomes and will consist of two components: (a) an in-person interview and questionnaires with the youth, and (b) usability and satisfaction ratings for the Qlarity app. Because every participant has unique needs, we have standardized guidelines that allow for minor modifications to our procedures when needed. For example, staff will read aloud questionnaires for participants who are nonreaders, and computer-assisted questionnaires will be available in hardcopy format. We will travel to participant residences or other locations to conduct the interviews as needed.

**Measures:** The following measures will be used to examine baseline demographic and pre- and post-changes in mindfulness skills, emotion regulation, and substance use: 1) Demographics, 2) Alcohol and Drug Use Survey, 3) Cigarette Use, 4) Adolescent Attitudes Questionnaire, 5) Emotion Regulation Scale, 6) Five Facet Mindfulness Questionnaire, 7) Youth Substance Use Interview (including Services Utilization), and 8) Qlarity usability and satisfaction rating. The Alcohol and Drug Use Survey is a 48-item scale that combines the Michigan Alcohol Screening Test (MAST) and the Drug Abuse Screening Test (DAST) and the Self-Efficacy for Limiting Substance Use. These scales are widely used as measures to assess the level and frequency of alcohol and drug use, use of mindfulness skills, as well as the ability to limit substance use, and have been shown to have good psychometric properties. In addition, urinary drug tests will be conducted at the baseline, 1- and 3-month follow ups. UA results will be photocopied after completion, and the UA cups will be discarded immediately; no identifying information will be recorded on the UA cups. We will use the same UA drug testing procedure that we have found to be successful in our current NIH funded study with adolescents in the juvenile justice system. All data will immediately be moved to a secure, locked location within ORI/Influents Innovations accessible only to the PI and research staff. The Services Utilization Survey is an interviewer-administered instrument that collects information about a respondent's use of a wide range of services such as in- and out-patient medical care (hospital, clinic, or office based), mental health treatment, drug and alcohol abuse treatment, and

Table 1. Measures		Assessments		
Measure	Baseline	1 Month	3 Month	
Adolescent Attitudes Questionnaire	●	●	●	
Alcohol and Drug Use Survey (MAST/DAST)	●	●	●	
Qlarity Usability and Satisfaction		●	●	
Cigarette Use	●	●	●	
Demographics	●			
Emotion Regulation Scale	●	●	●	
Five Facet Mindfulness	●	●	●	
Urine Drug Screens	●	●	●	
Youth Substance Use Interview (Services Utilization)	●	●	●	

health-related groups (e.g., Narcotics or Alcoholics Anonymous, or physical health groups). For each type of service accessed, there are questions regarding frequency, reason for the service (e.g., physical, mental health, substance-use related), insurance coverage and out-of-pocket expenses. The Five Facet Mindfulness Questionnaire is a 36-item self-reported questionnaire that queries aspects of mindfulness such as non-judgment. The Adolescent Attitudes Questionnaire is a measure of attitudes and beliefs regarding drug and alcohol that was adapted from an interview developed to test 12 mediators of drug use in adolescents. For this study, we will use the normative beliefs, lifestyle incongruence, beliefs about consequences, and commitment scales. The Emotion Regulation Scale is a 36-item self-report questionnaire designed to assess multiple aspects of emotion dysregulation. Program navigation and usability will be assessed for all participants and will include reports of: 1) ease of use, 2) perceived benefits of using the app, 3) likeability, and

4) suggestions for product development and modifications. Participants will provide ratings on product satisfaction and usability on a 7-point Likert Scale. Qualitative data gathered from the focus groups will be recorded and evaluated with the goal of identifying challenges to using the app, product satisfaction, and suggested product modifications. In addition to qualitative data gathered during the pilot evaluation study, login tracking information from the app will be used to assess each participant's: 1) frequency and duration of app use and 2) number of modules completed. These data will be used to evaluate treatment engagement and adherence.

**Statistical design and power overview:** This project will test the efficacy of the Qlarity app in Year 2 with a randomized trial that nests multiple assessments nested with 380 youth within each of two conditions. Half of the participants will receive the Qlarity app intervention and half will maintain business-as-usual. We hypothesize that Qlarity app will increase youth's emotional regulation, mindfulness and self-efficacy and decrease alcohol, tobacco, and other drug use. Within this study design, we will test for main effects, moderation, mediation, and acceptability of the Qlarity app intervention and expect to detect effect sizes of 0.25 standard deviations. Program feasibility will be demonstrated via significant pre-post differences, a high and consistent level of app use, and a high degree of youth satisfaction ratings. See Human Subjects Statistical Design and Power section for complete details.

**Feasibility benchmarks:** Program feasibility will be demonstrated by the achievement of the following benchmarks: (a) significant pre-post increases (e.g., Cohen's  $d > .35$ ) in emotional regulation, mindfulness, and self-efficacy, (b) significantly greater decreases in alcohol, tobacco, and other drug use for Qlarity participants; (c) a high consistent level of app usage (e.g., over 70% of users used the app at least 12 times over the 12 weeks); and (d) a high degree of youth satisfaction and ratings of app acceptability and usability (mean ratings  $> 4.0$  on the 5-point scale). Benchmarks are based on meta-analysis quantitative methods that recommend effect sizes of at least  $d > .25$  to demonstrate educationally meaningful change; a desire to show at least an average of weekly app use by a majority of participants; and a level of participant satisfaction that meets or exceeds that of Phase I.

